#### 2. TRIAL OBJECTIVES AND ENDPOINTS

#### 2.1 MAIN OBJECTIVES, PRIMARY AND SECONDARY ENDPOINTS

#### 2.1.1 Main objectives

The trial will investigate the safety and tolerability of BI 685509 in patients with CSPH in decompensated cirrhosis due to non-cholestatic liver diseases on top of standard of care. The primary objective is to estimate the percentage change in HVPG from baseline measured after 8 weeks in comparison to placebo. The primary analysis will be made for treated patients with baseline HVPG measurements (Full Analysis Set, FAS) as if all trial participants took treatment for the duration of the trial.

#### 2.1.2 Primary endpoint

The primary endpoint is the percentage change in HVPG from baseline (measured in mmHg) after 8 weeks of treatment.

#### 2.1.3 Secondary endpoints

Secondary endpoints include:

- occurrence of a response, which is defined as >10% reduction from baseline HVPG (measured in mmHg) after 8 weeks of treatment
- occurrence of further decompensation events (i.e. ascites, VH, and / or overt HE) during the 8-week treatment period
- occurrence of CTCAE grade 3 (or higher) hypotension or syncope based on Investigator judgement, during the 8-week treatment period
- occurrence of discontinuation due to hypotension or syncope during the 8-week treatment period

#### 2.2 FURTHER OBJECTIVES AND FURTHER ENDPOINTS

#### 2.2.1 Further objectives

In addition to the main objectives defined above, further objectives of this trial include an evaluation of general safety,

#### **2.2.2** Further endpoints

BI-VOD-12177 40-106 AD-03 (22.0)

#### Boehringer Ingelheim BI Trial No.: 1366-0055 c42374778-02 Clinical Trial Protocol

Page 32 of 98

#### 3. **DESCRIPTION OF DESIGN AND TRIAL POPULATION**

#### 3.1 **OVERALL TRIAL DESIGN**

This phase 2 multi-national, randomised, placebo-controlled and parallel group trial to investigate the effects of oral BI 685509 on portal hypertension after 8 weeks treatment in patients with clinically significant portal hypertension (CSPH) in decompensated cirrhosis after the first decompensation event, who are stabilized (CTP 5-7).

Trial participants will be enrolled in the trial and screened for eligibility once they have signed the informed consent. The screening period consists of up to 2 visits (Visits 1a and b) and will last a maximum of 4 weeks. Trial participants will be able to progress from one visit to the next when eligibility of the previous visit is confirmed. Assessments will include ultrasound of the liver and spleen, and measurement of HVPG. Trial participants who remain eligible and who successfully complete this period will proceed to the 8-week randomised, placebo-controlled treatment period.

In total, 40 trial participants will be randomized in a 1:1 ratio, with 20 trial participants in the active treatment arm, and 20 trial participants in the placebo arm. The randomization will be stratified by use (or not) of NSBBs / carvedilol and type of first decompensation event (ascites or variceal haemorrhage).

Following randomization at visit 2, trial participants will begin the intake of trial medication(s) and will enter a dose-titration period of BI 685509 or matching placebo. If the dose is tolerated, one week later (at Visit 3, day 8), the dose for all will be up-titrated to BID 685509 or matching placebo. If this dose is tolerated, a second up-titration to BID BI 685509 or matching placebo will occur after another week (at Visit 4, day 15). Following the dose-titration period, and if the dose is tolerated, trial participants will remain on the highest dose of BI 685509 for the remainder of the treatment period until they reach the End of Treatment (EoT) visit and 8 weeks of treatment. If the dose is not tolerated, trial medication may be interrupted or the dose can be reduced / down-titrated.

The ultrasound and and the HVPG measurement will be repeated during the treatment period (refer to Figure 3.1: 1).

After the 8 week treatment period all trial participants will enter a 2 week follow-up period without trial medication. The trial participant's participation in the trial will be complete when they have performed the last planned visit (i.e. End of Study [EoS], 2 weeks after EoT).

#### Boehringer Ingelheim BI Trial No.: 1366-0055 c42374778-02 Clinical Trial Protocol

Page 34 of 98

Proprietary confidential information © 2023 Boehringer Ingelheim International GmbH or one or more of its affiliated companies

Figure 3.1: 1 Trial design schematic

# **3.2** DISCUSSION OF TRIAL DESIGN, INCLUDING THE CHOICE OF CONTROL GROUP(S)

A randomised, double-blind, placebo-controlled and parallel group design has been chosen for this trial, on top of standard of care. The randomised double-blind design will control for assignment bias. Placebo as control was chosen to show the efficacy of BI 685509 compared to placebo plus standard of care.

A treatment duration of 8 weeks has been chosen to allow an evaluation of short-term efficacy and indirect comparison to the week 8 results from trials 1366-0021 and 1366-0029.

The trial participant population of this trial has been chosen as it represents the intended patient population to be treated with for BI 685509 (patients with clinically significant portal hypertension in decompensated cirrhosis due to non-cholestatic liver diseases).

For details regarding the choice of renal function in the patient population, refer to Section 1.2.

The measurement of HVPG was chosen as the primary endpoint as it is the gold standard to estimate portal venous pressure in trial participants with cirrhosis, i.e. assessing the severity of sinusoidal PH [R20-4090]. It is used as an established surrogate marker for improvement and / or worsening of liver fibrosis / function, since a decrease in HVPG translates into a clinically meaningful benefit [R20-1204]. The prognostic value of HVPG has been underlined by several landmark studies, showing that an HVPG  $\geq$  10 mmHg (i.e. CSPH) is predictive of the formation of varices [R20-4092], while a (pharmacologically-induced) decrease of HVPG modulates the respective risk of variceal growth and decompensation [R20-4093, R20-4091]. Hence, this also explains the choice of the secondary endpoint relating to the occurrence of further decompensation events (refer to Section 2.1.3). Other secondary endpoints (occurrence of significant hypotension or syncope, and occurrence of discontinuation due to hypotension or syncope) were chosen as they are relevant based on the mechanism of action of BI 685509.

Trial participants will be screened for the trial based on the eligibility criteria (refer to Sections 3.3.2 and 3.3.3). At Visit 1b (the final visit within the screening period) trial participants who remain eligible following Visits 1a will undergo their first HVPG measurement.

Non-invasive assessments (i.e. ultrasound and

have been chosen as part of the screening procedures to further investigate the trial participants' status, to establish baseline values for comparison with treatment, and to gain further insight into the use of non-invasive methods to investigate liver function and portal pressure. These assessments will be repeated (refer to Figure 3.1: 1 and the Flow Chart) to assess a time-dependency of the treatment.

Following randomisation, the trial design includes a dose-titration period. The mechanism related vasodilatation of BI 685509 can lead to orthostatic dysregulation and hypotensive episodes (refer to Table 1.4.2: 1). The orthostatic dysregulation is dose-limiting and clinical tolerability is improved if the dose is titrated. A BID administration also allows the total daily exposure of BI 685509 to be further increased while high peak concentrations are avoided. Hence, in this trial, a dose-titration regimen of BID to BID to BID to BID will be followed.

Trial participants selected for this trial have a risk for further decompensation. A DMC, independent from the Sponsor, will therefore be established to review safety data at intervals to identify any potential risks and / or the need for implementation of further safety measures. The tasks and responsibilities of the DMC members will be detailed in the DMC charter (refer to Section 8.7).

An independent AC will also be established for adjudication of hepatic injury. The tasks and responsibilities of the AC members will be detailed in the AC charter (refer to Section 8.7).

#### **3.3** SELECTION OF TRIAL POPULATION

40 trial participants with CSPH in decompensated cirrhosis due to non-cholestatic liver disease will be randomized into the trial. Approximately 20 sites are planned across multiple countries. It is anticipated that 2 trial participants will be randomised at each site. If enrolment is delayed, additional sites may be recruited.

Screening of trial participants for this trial is competitive, i.e. screening for the trial will stop at all sites at the same time once a sufficient number of trial participants have been screened to deliver the required number of randomised trial participants. Investigators will be notified about the screening completion and will then not be allowed to screen additional trial participants for this trial. Trial participants already in screening at this time will be allowed to continue to randomisation if eligible.

Re-testing during the screening period is allowed once (e.g. if the Investigator believes an ineligible laboratory test is the result of an error or extenuating circumstances, the test can be repeated once without the trial participant having to be re-screened). Re-screening is also allowed once provided that the reasons for screen failure were reversible and have been resolved, based on Investigator judgement. A trial participant is considered a "re-screener" if

he / she was not eligible for the trial initially and is subsequently re-screened, going through the informed consent process for a second time, receiving a new unique trial participant number and repeating the screening period assessments.

A log of all trial participants enrolled into the trial (i.e. who have signed the informed consent) will be maintained in the Investigator Site File (ISF) irrespective of whether they have been treated with investigational drug or not.

If retrospectively it is found that a patient has been randomized in error (=did not meet all inclusion criteria or met one or more exclusion criteria), the sponsor or delegate should be contacted immediately. Based on an individual benefit-risk assessment a decision will be made whether continued trial participation is possible or not.

This trial will include an option for participants to complete anonymized questionnaires to provide feedback on their clinical trial experience. Providing this feedback is not required for trial participation, and information collected from these questionnaires will not be analysed as part of the clinical data for the trial (see Section 10.4)

#### 3.3.1 Main diagnosis for trial entry

The trial will include trial participants with decompensated cirrhosis due to non-cholestatic liver disease after the first decompensation event, who are stabilized (CTP 5-7).

Please refer to Section  $\underline{8.3.1}$  (Source Documents) for the documentation requirements pertaining to the in- and exclusion criteria.

#### 3.3.2 Inclusion criteria

- 1. Signed and dated written informed consent in accordance with ICH-GCP and local legislation prior to admission to the trial
- 2. Male or female who is  $\geq 18$  (or who is of legal age in countries where that is greater than 18) and  $\leq 75$  years old at screening (Visit 1a)
- 3. Diagnosis of cirrhosis due to non-cholestatic liver disease (including HCV, HBV, NASH, alcohol-related liver disease, autoimmune hepatitis, Wilson's disease, haemachromatosis, alpha-1 antitrypsin [A1At] deficiency)
- 4. One previous clinically significant decompensation event with clinical resolution at least 4 weeks prior start of screening (visit 1a):
  - a. First variceal haemorrhage
  - b. First episode of clinically significant ascites (requiring intervention in lifestyle [fluid and salt restriction] or medical treatment)
- 5. Willing and able to undergo HVPG measurements per protocol (based on Investigator judgement)
- 6. If receiving statins must be on a stable dose for at least 3 months prior to screening (Visit 1b), with no planned dose change throughout the trial
- 7. If receiving treatment with NSBBs or carvedilol must be on a stable dose for at least 1 month prior to screening (Visit 1b), with no planned dose change throughout the trial
- 8. For patient with alcohol-related cirrhosis, abstinence from significant alcohol misuse / abuse for a minimum of 2 months prior to screening (Visit 1a), and the ability to abstain from alcohol throughout the trial (both evaluated based on Investigator judgement)
- 9. WOCBP must be ready and able to use highly effective methods of birth control per ICH M3 (R2) that result in a low failure rate of less than 1% per year when used consistently and correctly from the randomisation visit (Visit 2) until 7 days after the last treatment in this trial. The patient must agree to periodic pregnancy testing during participation in the trial. Refer to Section 4.2.2.3 and the patient information for a list of contraception methods meeting these criteria
- 10. Men able to father a child and who have a female sexual partner of CBP, must use a condom with or without spermicide, or adopt complete sexual abstinence, or be vasectomised (with appropriate post-vasectomy documentation of the absence of sperm in the ejaculate), from the randomisation visit (Visit 2) until 7 days after the last treatment in this trial. Refer to Section 4.2.2.3 and the patient information for further details

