#### **1.3 RATIONALE FOR PERFORMING THE TRIAL**

In this Phase 2 trial, the efficacy of treatment in patients with CSPH (defined by HVPG  $\geq 10$  mmHg) in decompensated cirrhosis due to non-cholestatic liver diseases will be assessed. The trial will serve to evaluate short-term efficacy of BI 685509 and will also provide supportive evidence for the planned Phase 2I development together with trials 1366-0021 and 1366-0029. The data of this trial will be indirectly compared with the data from trials 1366-0021 and 1366-0029.

In order to be able to address future scientific questions, patients will be asked to voluntarily donate biospecimens for banking (please see Section 5.5). If the patient agrees, banked samples may be used for future biomarker research and drug development projects, e.g. to identify patients that are more likely to benefit from a treatment or experience an adverse event (AE), or to gain a mechanistic understanding of drug effects and thereby better match patients with therapies.

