**Boehringer Ingelheim** 

- 13. Alpha-fetoprotein >50 ng/mL (>50  $\mu$ g/L) at screening (Visit 1a), measured by the central laboratory
- 14. Prior orthotopic liver transplantation
- 15. Prior or planned TIPS or other porto-systemic bypass procedure during the trial conduct
- 16. Known portal vein thrombosis
- 17. History of clinically relevant orthostatic hypotension, fainting spells or blackouts due to hypotension or of unknown origin (based on Investigator judgement)
- 18. QTcF-interval >450 ms in men or >470 ms in women at screening (Visit 1a), a family history of long QT syndrome, or concomitant use of therapies with a known risk of Torsade de Pointes or planned initiation of such therapies during the trial (refer to Section 4.2.2.1)

Page 39 of 98

Proprietary confidential information © 2023 Boehringer Ingelheim International GmbH or one or more of its affiliated companies

- 19. Contraindication to any of the trial assessments (e.g. poor patient co-operation for HVPG,
- 20. Major surgery (major according to the investigator's assessment) performed within 12 weeks prior to randomisation (Visit 2) or planned during the trial, e.g. hip replacement.
- 21. Any documented active or suspected malignancy or history of malignancy within 5 years prior to screening (Visit 1a), except appropriately treated basal cell carcinoma of the skin or in situ carcinoma of uterine cervix
- 22. History of (in the 6 months prior to randomisation [Visit 2]), or ongoing, chronic drug abuse, or not expected to comply with the protocol requirements for any other reason that, based on Investigator judgement, makes the patient an unreliable trial recruit or unlikely to complete the trial as scheduled
- 23. Previous randomisation in this trial, previous exposure to BI 685509, or an allergy / contraindication to BI 685509 and matching placebo / or any of their excipients
- 24. Currently enrolled in another investigational device or drug trial, or less than 30 days or 5 half-lives (whichever is longer) prior to randomisation (Visit 2) since ending another investigational device or drug trial, or receiving other investigational treatment(s)
- 25. Women who are pregnant, nursing, or who plan to become pregnant while in the trial
- 26. Any other medical condition that, based on Investigator judgement, poses a safety risk for the patient or may interfere with the objectives of the trial

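### The protocol defines its CSPH population by HVPG of at least 10 mmHg, but no eligibility criterion uses the HVPG measured at Visit 1b

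*Protocol*

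**What the plan says.** **Population.** Protocol Section 1.3 sets out to assess "the efficacy of treatment in patients with CSPH (defined by HVPG", and the bracket goes on to give a threshold of at least 10 mmHg. Section 5.1.1 repeats that threshold where it summarises the HVPG procedure. Section 3.3 then states: "40 trial participants with CSPH in decompensated cirrhosis due to non-cholestatic liver disease will be randomized into the trial". The synopsis and Section 3.1 describe the population in the same way.

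**Entry rules.** Section 3.3.1 gives the main diagnosis: "The trial will include trial participants with decompensated cirrhosis due to non-cholestatic liver disease after the first decompensation event", stabilised at Child-Turcotte-Pugh 5-7. It mentions neither CSPH nor HVPG. Two of the 36 criteria name HVPG:
- Inclusion 5 (Section 3.3.2): "Willing and able to undergo HVPG measurements per protocol (based on Investigator judgement".
- Exclusion 19 (Section 3.3.3): "Contraindication to any of the trial assessments (e.g. poor patient co-operation for HVPG".

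Both concern whether the test can be done. Neither concerns its result.

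**Timing.** Under Section 3.2, at Visit 1b, "trial participants who remain eligible following Visits 1a will undergo their first HVPG measurement". The Flow Chart reviews the criteria at Visits 1a, 1b and 2. Its footnote 1 lets a participant move on once all results of the previous visit are available and he or she is still eligible. Under Section 5.1.1 the Visit 1b tracing is read both locally and centrally, and the central read is the official one.

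**SAP.** Section 6.4 takes over the protocol's analysis sets. Section 4 records that the programme was stopped in May 2024 with no Week 8 HVPG collected, and that the HVPG analyses will not be done.

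**The concern.** The trial states its target population by a measurement, takes that measurement before randomisation, and then has no rule that uses it. Followed to the letter, the plan can randomise people who fall outside its own definition.

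Three things would be at stake:
- **Whom the estimate describes.** The objective, the benefit-risk statement in Section 1.4.3 and the planned indirect comparison with trials 1366-0021 and 1366-0029 (Sections 1.3 and 3.2) are all built around patients with CSPH.
- **The endpoint scale.** The primary endpoint is a percentage of baseline HVPG, and the responder endpoint is a reduction of more than 10%. The lower the baseline, the smaller the absolute change needed to count as a response.
- **The trial's size.** With 20 per arm, each participant carries visible weight.

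**Working it through.** **1. Could a threshold be present elsewhere, or blacked out?** The inclusion criteria run 1-10 and the exclusion criteria 1-26 without a numbering gap. The text missing from exclusion 19 follows an example of a contraindication to an assessment. The main criteria in the synopsis add no threshold. Redaction is not a plausible explanation.

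**2. Does another rule catch HVPG below 10 mmHg?**

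| Place | What it requires | Stops a low HVPG? |
|---|---|---|
| Flow Chart and footnote 1 | Criteria reviewed at Visits 1a, 1b and 2, with results available | No; there is no criterion to apply the result to |
| Section 3.3, randomised in error | A listed inclusion criterion not met, or an exclusion criterion met | No; nobody fails a criterion on the HVPG value |
| Exclusion 26 | Investigator judgement on another medical condition | Not as a rule; discretionary, and HVPG is not named |
| Section 7.2.1, FAS | At least one dose and a recorded baseline | No; any baseline value qualifies |
| SAP Table 7.1: 1 | Baseline HVPG summarised at ≤12 / >12 and ≤15 / >15 | No; there is no cut at 10, so such participants would not be shown separately |

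**3. Can a participant with a qualifying first event measure below 10 mmHg at entry?** The protocol does not rule it out. Inclusion 4 requires clinical resolution of the event at least 4 weeks before screening. Inclusion 7 allows a stable dose of NSBB or carvedilol. The documents do not say how often this would happen.

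**4. The plan's own figure.** Section 7.5 states an 89.3% probability of observing an effect of at least 10% when the true reduction is 20%. With SD 25% and 20 per group, the standard error of the difference is 25 × √(2/20) = 7.906, and (20 − 10)/7.906 = 1.265. A t distribution with 38 degrees of freedom gives 89.3%, which reproduces the figure. No baseline HVPG enters this calculation, so it neither supports nor contradicts the point.

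**5. Effect on the percentage scale.** Percentage change for a fall of d mmHg from baseline B is 100 × d/B. A response (>10%) needs d > 0.10 × B.

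| Baseline B (mmHg) | A 1 mmHg fall, 100/B | Fall that must be exceeded, 0.10 × B |
|---|---|---|
| 16 | 6.3% | 1.6 mmHg |
| 12 | 8.3% | 1.2 mmHg |
| 10 | 10.0% (not a response) | 1.0 mmHg |
| 9 | 11.1% | 0.9 mmHg |
| 8 | 12.5% | 0.8 mmHg |

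A 1 mmHg fall is a response exactly when B is below 10 mmHg. The table changes smoothly, with no step at 10.

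**6. Weight of one participant.** 1/20 = 5% of an arm, and 1/40 = 2.5% of the trial.

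**The case against.** The strongest reply is that entry is deliberately clinical. Inclusion 4 requires a variceal haemorrhage or clinically significant ascites. Section 1.1 holds portal hypertension responsible for most complications of cirrhosis, and Section 3.2 links HVPG of at least 10 mmHg to the formation of varices. On that view the qualifying event stands in for CSPH, and a threshold would add little beyond screen failures. This stands as far as frequency goes: most participants would probably meet the definition. It does not remove the gap, because the protocol defines CSPH by the measured gradient, the event must have resolved, and NSBB or carvedilol may continue.

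There is also mitigation on the endpoint. Baseline HVPG is a covariate in the ANCOVA (Section 7.2.3). Pressures are taken in triplicate and read centrally. Responses produced by noise can arise in both randomised arms. No hypothesis is tested. All of this stands and limits the damage.

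A reader might infer more than the documents support:
- **That low baselines inflate the variance or bias the comparison.** The documents give no measurement error and no baseline distribution, so this cannot be calculated.
- **That the 89.3% in Section 7.5 would fall by a known amount.** That needs both a share below 10 mmHg and an assumed effect in those participants. The documents give neither.
- **That cure of HCV or stopping alcohol is required of everyone and lowers HVPG at entry.** Exclusion 3 applies only to those who received curative HCV therapy. Inclusion 8 applies only to alcohol-related cirrhosis, and before screening it asks for 2 months without significant misuse.

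**Conclusion.** The point holds as an inconsistency between the stated population and the eligibility criteria. The absence of the criterion is certain from the text. The practical size is not known: each affected participant is 5% of an arm, but the documents give no basis for a count, and it may be zero or very few. On the endpoint, a 1 mmHg fall counts as a response at any baseline below 10 mmHg and at none from 10 mmHg up. This is the lower end of a continuous property of percentage endpoints and does not start at the threshold.

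A reader might also infer that the reported results are affected. They are not, because SAP Section 4 cancels every HVPG analysis. This is a defect in the protocol's design, relevant if the design is restarted or reused. It should be corrected, but it would not by itself invalidate the trial.

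**What to change.** Reconcile Sections 3.3.1 and 3.3.2 with the definition in Section 1.3, in one of two ways:

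1. **Keep the CSPH population.** Make the protocol's own CSPH definition, applied at Visit 1b, an eligibility criterion. State whether the local or the central read decides. Section 5.1.1 foresees the two disagreeing at Visit 1b, so a criterion based on the local read can still admit someone whose official baseline is below the definition. State in advance how that participant is analysed. If the local read decides, also require it to be documented before randomisation: Section 5.1.1 says it goes into the source documents and eCRF but not when.
2. **Keep the clinical entry route.** Describe the population as decompensated cirrhosis after a first event, and drop the claim that all randomised participants have HVPG-defined CSPH.

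For either option, a baseline HVPG category split at 10 mmHg in the SAP would show how many participants fall on each side.

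**Cost.** No new procedure is needed, because HVPG is already measured before randomisation. Option 1 adds screen failures after an invasive test. If a share s of otherwise eligible participants falls below the definition, about 40/(1 − s) must be measured. For scale only, s = 5% gives 40/0.95 ≈ 42 and s = 15% gives 40/0.85 ≈ 47, so about 2 to 7 extra procedures. Both shares are assumptions without a source in the documents. Option 2 costs only wording, but weakens the indirect comparison with a trial that the protocol describes as conducted in CSPH (1366-0021, Section 4.1.2).
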